8 STUDY ASSESSMENTS AND PROCEDURES

8.1 SCREENING PROCEDURES

8.1.1 Screening activities performed prior to obtaining informed consent

A waiver of consent (per section 10.1.1) is requested for the following screening activities as the following are minimal risk activities and can be performed before the subject has signed a consent:

- Email, written, in person or telephone communications with prospective subjects.
- Review of existing medical records to include H&P, laboratory studies, etc.
- Review of existing MRI, x-ray, or CT images.
- Review of existing photographs or videos.
- Review of existing pathology specimens/reports from a specimen obtained for diagnostic purposes.

8.1.2 Screening activities performed after a consent for screening has been signed

The following activities will be performed only after the subject has signed the consent this study. Assessments performed at outside facilities or on another NIH protocol within the timeframes below may also be used to determine eligibility once a participant has signed the consent.

- Measurement of blood leptin concentration

8.2 EFFICACY ASSESSMENTS

1. Evaluation of diabetes control (7 mL): HbA1c, fasting C-peptide and insulin.

2. Oral Glucose Tolerance Test: After an overnight fast preceding the test, subjects will be given 75-gram (1.75gm/kg up to 44kg) oral glucose solution. Venous glucose, plasma insulin and C-peptide (3 cc blood to be drawn at each draw) will be obtained from blood samples drawn at -10, 0, 30, 60, 90, 120 and 180 minutes during the oral glucose tolerance test. The area under the glucose, insulin and C-peptide.

8.2.1 Clinical Evaluations

1. Diabetes related antibodies (4 cc; first visit only)
2. Physical Examination: This will be performed at each visit and will incorporate a standard physical examination with special emphasis on skin exam and dysmorphic features. Pubertal exam (including examination of breasts and external genitalia) will be performed as age appropriate.

Abbreviated Title: Effects of leptin in insulin resistance

Version Date: AM N ver. (approved 10/21/20); rev for AM O (5/5/21)

3. Vital Signs: Height in cm, weight in kg and blood pressure, BMI, resting pulse, temperature in degrees Celsius.
4. Biochemical evaluation (3 cc): This will include basic chemistry, liver panel, and mineral panel and cystatin C.
5. Hematological evaluation (3 cc): This will include determination of CBC with differential white count analysis.
6. Urine studies: This will include urinalysis and 24 hr urine for protein, microalbuminuria, minerals, uric acid, creatinine and creatinine clearance.
7. Lipid profile (3 cc): Levels of fasting triglyceride, total cholesterol, LDL cholesterol, HDL cholesterol, lipoprotein profile, free fatty acid, and lipoprotein profile will be obtained. These will be drawn after an overnight fast.
8. Hormonal evaluation (12 cc): This will include measurement of reproductive hormones (i.e. sex steroids, gonadotropins), assessment of the growth hormone axis (i.e. IGF-1, GH, IGF binding proteins), bone health and turnover markers (i.e. osteocalcin, PTH, Vitamin D), thyroid function tests.
9. Inflammatory markers (2 cc): This will include ESR and hsCRP.
10. Leptin concentration (part of 10 cc research blood collection): Leptin concentrations will be determined will be done after a overnight fast.
11. Ultrasound of pelvis: This will be performed on the female patient to evaluate the effects of hyperinsulinism and hyperandrogenism on the uterus and ovaries.
12. Ultrasound of the thyroid: This will be performed to screen for possible papillary thyroid carcinoma (PTC) or other possible thyroid structural abnormalities since this patient population may be at a higher risk of developing PTC. The testing may also uncover information for future analysis. Subjects will have an ultrasound of their thyroid performed with their baseline visit and at routine NIH follow-up visits, as clinically indicated.

8.2.2 Biospecimen Evaluations

Biological specimen collection and laboratory evaluations

See Section 8.2 and 8.2.1 for details.

Research blood samples: The amount of blood that may be drawn from adult patients and volunteers (i.e., those persons 18 years of age or older) for research purposes shall not exceed 10.5 mL/kg or 550 mL, whichever is smaller, over any eight-week period.

Abbreviated Title: Effects of leptin in insulin resistance

Version Date: AM N ver. (approved 10/21/20); rev for AM O (5/5/21)

For pediatric patients, no more than 5 mL/kg may be drawn for research purposes in a single day, and no more than 9.5 mL/kg may be drawn over any eight-week period.

8.2.3 Correlative Studies for Research/Pharmacokinetic Studies

Special assays or procedures required

See Section 8.2.1 for leptin assays.

8.2.4 Samples for Genetic/Genomic Analysis

8.2.4.1 Description of the scope of genetic/genomic analysis

None

8.2.4.2 Description of how privacy and confidentiality of medical information/biological specimens will be maximized

N/A

8.2.4.3 Management of Results

N/A

8.2.4.4 Genetic counseling

N/A

8.3 SAFETY AND OTHER ASSESSMENTS

See Section 8.4

- Pregnancy tests will be performed at each visit in female patients with reproductive capacity.

Results of all clinical tests reported in the patient's NIH medical record and will be provided to and discussed with subjects.

8.4 ADVERSE EVENTS AND SERIOUS ADVERSE EVENTS

8.4.1 Definition of Adverse Event

Adverse event means any untoward medical occurrence associated with the use of an intervention in humans, whether or not considered intervention-related (21 CFR 312.32 (a)).

8.4.2 Definition of Serious Adverse Events (SAE)

An adverse event (AE) or suspected adverse reaction is considered "serious" if, in the view of either the investigator or sponsor, it results in any of the following outcomes: death, a life-threatening adverse event, inpatient hospitalization or prolongation of existing hospitalization, a persistent or significant incapacity or substantial disruption of the ability to conduct normal life functions, or a congenital anomaly/birth defect. Important medical events that may not result in death, be life-threatening, or require hospitalization may be considered serious when, based upon appropriate medical judgment, they may jeopardize the participant and may require medical or surgical intervention to prevent one of the outcomes listed in this definition. Examples of such medical events include allergic bronchospasm requiring intensive treatment in an emergency

Abbreviated Title: Effects of leptin in insulin resistance

Version Date: AM N ver. (approved 10/21/20); rev for AM O (5/5/21)

room or at home, blood dyscrasias or convulsions that do not result in inpatient hospitalization, or the development of drug dependency or drug abuse.

8.4.3 Classification of an Adverse Event

8.4.3.1 Severity of Event

The following guidelines will be used to describe AE severity.

- **Mild** – Events require minimal or no treatment and do not interfere with the participant’s daily activities.
- **Moderate** – Events result in a low level of inconvenience or concern with the therapeutic measures. Moderate events may cause some interference with functioning.
- **Severe** – Events interrupt a participant’s usual daily activity and may require systemic drug therapy or other treatment. Severe events are usually potentially life-threatening or incapacitating. Of note, the term “severe” does not necessarily equate to “serious”.

8.4.3.2 Relationship to Study Intervention

All adverse events (AEs) must have their relationship to study intervention assessed by the investigator who examines and evaluates the participant based on temporal relationship and his/her clinical judgment. The degree of certainty about causality will be graded using the categories below. In a clinical trial, the study product must always be suspect.

- **Related** – The AE is known to occur with the study intervention, there is a reasonable possibility that the study intervention caused the AE, or there is a temporal relationship between the study intervention and event. Reasonable possibility means that there is evidence to suggest a causal relationship between the study intervention and the AE.
- **Not Related** – There is not a reasonable possibility that the administration of the study intervention caused the event, there is no temporal relationship between the study intervention and event onset, or an alternate etiology has been established.

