In accordance with the requirements of 21 CFR 312.32, the PI or designee will report all SAEs, whether or not these are considered related to the investigational drug or study intervention, that occur throughout the study to the Sponsor, including those events listed in the protocol or Investigator's Brochure as anticipated to occur, as follows:

Deaths: within 24 hours of the investigator's awareness

All other SAEs: within 48 hours of the investigator's awareness

All AEs will be sent to the Sponsor quarterly, or at minimum annually, for submission to the FDA in the IND Annual Report.

The PI will immediately report all deaths and SAEs to the Sponsor by disclosing all event-related information in a completed MedWatch Form 3500A. This form should include the IND number, protocol number, PI name, and an assessment on the reasonable possibility of a relationship between the event and the study drug or intervention. The completed MedWatch Form 3500A will be sent to the Clinical Director/CEO and/or designated medical monitor with a copy to the NIH Office of Research Support & Compliance (ORSC) Regulatory Support Section.

The CEO and/or designee will be responsible for determining whether the event is reportable to the FDA as an IND Safety Report if it is a serious, unexpected, and suspected adverse reaction (SUSAR). If the sponsor determines the SAE meets the criteria of a SUSAR, the ORSC will submit an Initial IND Safety Report to the FDA no later than 15 calendar days after the PI's notification of the event to the Sponsor. Deaths or life-threatening events will be reported to the FDA no later than 7 calendar days after the PI's notification of the event to the Sponsor. The Sponsor will submit any relevant additional information in a Follow-up IND Safety Report no later than 15 calendar days after receiving the information. All SAEs will be monitored until satisfactory resolution. All AEs and SAEs will be documented on appropriate study records.

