8.5 UNANTICIPATED PROBLEMS

8.5.1 Definition of Unanticipated Problems (UP)

Any incident, experience, or outcome that meets all of the following criteria:

- Unexpected in terms of nature, severity, or frequency given (a) the research procedures that are described in the protocol-related documents, such as the Institutional Review Board (IRB)-approved research protocol and informed consent document; and (b) the characteristics of the participant population being studied; and
- Related or possibly related to participation in the research (“possibly related” means there is a reasonable possibility that the incident, experience, or outcome may have been caused by the procedures involved in the research); and
- Suggests that the research places participants or others (which many include research staff, family members or other individuals not directly participating in the research) at a greater risk of harm (including physical, psychological, economic, or social harm) than was previously known or expected.

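### The two causality categories in section 8.4.3.2 are not mutually exclusive: an on-treatment event with another cause can be both Related and Not Related

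*Combined protocol and SAP*

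**What the plan says.** Section 8.4.3.2 has the examining investigator grade every adverse event from its timing and from clinical judgment, using two categories.

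- **Related** has three alternatives. The first two are "The AE is known to occur with the study intervention, there is a reasonable possibility that the study intervention caused the AE". The third follows: "or there is a temporal relationship between the study intervention and event". The section explains a reasonable possibility as evidence that suggests causation.
- **Not Related** also has three alternatives. The first is "There is not a reasonable possibility that the administration of the study intervention caused the event". The other two are "there is no temporal relationship between the study intervention and event onset, or an alternate etiology has been established".

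The section adds that the study product should always be under suspicion. It gives no time window for a temporal relationship and no order of precedence between the categories.

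Section 9.4.4 captures relationship to study drug for each event. Section 8.4.6 requires the SAE form sent to the sponsor to carry "an assessment on the reasonable possibility of a relationship between the event and the study drug or intervention". It also asks for SAEs after the collection period to be reported when they are believed related to study drug or to a protocol-specified procedure.

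**The concern.** Both lists are joined by *or*, so each condition is sufficient by itself. The condition that places an event in one category does not exclude it from the other. An event that begins on treatment and has a documented other cause is Related by its timing and Not Related by its cause. Two assessors can apply the text faithfully and record opposite grades.

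This matters more than usual because the trial is single-arm (section 4.2). No comparator rate is available to show how much of the recorded harm belongs to the underlying disease. The relationship field is one of the few items that bears on that question. If its value depends on which list the assessor reads first, counts of related events cannot be interpreted or compared between assessors. The same judgment also decides whether a late SAE is reported at all under section 8.4.6.

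**Working it through.** The plan states no figure on this point, so there is none to reproduce. There are three checks.

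**1. Do the definitions overlap as written?** Take four yes/no conditions from section 8.4.3.2: K (known to occur with the drug), P (reasonable possibility of causation), T (temporal relationship), A (alternate etiology established).

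- Related = K or P or T
- Not Related = (not P) or (not T) or A

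There are 2 × 2 × 2 × 2 = 16 combinations.

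- Related fails only when K, P and T are all absent: 2 combinations (A either way), both Not Related only.
- Not Related fails only when P and T are present and A is absent: 2 combinations (K either way), both Related only.
- No combination meets neither definition.
- Both definitions are met in 16 − 2 − 2 = **12**.
- Among the 8 combinations with T present, all 8 are Related and 8 − 2 = **6** are also Not Related.

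Some combinations may be thought incoherent. Suppose an established other cause is taken to rule out a reasonable possibility. The 4 combinations with both P and A then drop out, 2 of them with T present. All 4 had met both definitions. That leaves 12 − 4 = 8 of 12 overlapping, and 6 − 2 = 4 of 6 where T is present. The remaining core is T present with P absent: Related on timing, Not Related for want of a reasonable possibility.

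An example: hypoglycemia is listed in section 2.3.1 as a risk of the drug in insulin-treated patients. A hypothetical on-treatment episode traced to an insulin dosing error meets K and T, so it is Related. It also meets A, so it is Not Related.

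**2. How far could the timing condition reach?** Dosing is every 12 hours, with once daily possible after a year (6.1.2), for 12 months or longer (1.1). Events are recorded from consent until 7 days (non-serious) or 30 days (SAEs) after the last day of participation (8.4.4). Assume 4 days between consent and first dose, the upper end of the 3–4 day baseline stay, and 365 days on drug. The share of recording time spent on drug is:

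- non-serious: 365 / (365 + 4 + 7) = 97.1%
- SAEs: 365 / (365 + 4 + 30) = 91.5%

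With 1 to 7 pre-dose days the ranges are 96.3–97.9% and 90.8–92.2%. These are shares of time, not of events. They matter only if a temporal relationship means onset while on drug.

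**3. Do the AE field and the SAE form use the same test?** Section 8.4.6 asks only about reasonable possibility. They can disagree in two directions:

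- Timing fits but there is no reasonable possibility: the AE field can say Related while the SAE form says no.
- A reasonable possibility is judged to exist but an alternate etiology is also recorded: the SAE form says yes while the AE field can say Not Related.

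**The case against.** The strongest reply is that section 8.4.3.2 asks for clinical judgment and is not a mechanical rule. A temporal relationship is undefined and may mean a plausible time course, not mere onset on drug. An experienced investigator would not grade everything Related, and the reminder to keep the drug under suspicion leans one way in doubtful cases. This limits the reach of the problem but does not remove it. Judgment used to choose between two satisfied definitions is exactly what will vary between assessors, and the reminder does not say which category wins.

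Several stronger readings are tempting and should not be drawn:

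- **Nearly every event will be Related.** This needs the onset-on-drug reading, which the documents do not state.
- **A numerical range for the related share.** This would need the proportion of events with another cause, which the documents do not give. Any such range only restates the assumed proportion.
- **Diabetic complications are described as common.** Section 2.2 names them among causes of death in the most severe patients and gives no frequency.
- **SAE reporting is compromised.** SAEs within the collection period go to the sponsor whether or not they are considered related (8.4.6, 10.5), and the sponsor side decides which are expedited.
- **The unanticipated-problem definition should be tied to the same test.** In section 8.5.1, possibly related "means there is a reasonable possibility that the incident, experience, or outcome may have been caused by the procedures involved in the research". That covers research procedures, and a metreleptin-only test would narrow it.

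**Conclusion.** The definitions are wrong as written, and the consequence is modest. The overlap follows from the wording alone: 12 of 16 logical combinations meet both categories, and nothing in the protocol resolves the conflict. Its practical reach depends on how a temporal relationship is read. If it means onset on drug, any on-treatment event with another cause can fall in both categories.

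The harm has two parts. The relationship field under section 9.4.4 loses consistency and interpretability in a trial without a control group, and the late-SAE rule in section 8.4.6 rests on an ambiguous term. In-window SAE reporting, the efficacy analysis and power are not affected.

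**What to change.** Amend section 8.4.3.2 as follows.

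- **Related:** there is a reasonable possibility that the study intervention caused the event, meaning evidence that suggests causation, including a known effect of the drug. Timing supports the judgment but is not sufficient alone.
- **Not Related:** all other events, with the alternate etiology recorded where there is one.
- Doubtful cases are graded Related, in keeping with the section's stance on the study product.

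State in section 8.4.6 that the SAE form uses this same test. Leave section 8.5.1 unchanged.

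Apply the definition prospectively, and mark in AE summaries which events were graded under the present protocol definitions. Mandatory re-grading is not needed. Section 8.4.3.2 relies on the investigator who examined the participant, and re-grading old events would rest on records with outcomes already known.

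The cost is a few lines in an amendment. The downside is that related counts before and after it are not directly comparable, which matters because 11 participants are already enrolled (section 5.6).

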8.4.3.3 Expectedness

The PI will be responsible for determining whether an adverse event (AE) is expected or unexpected. An AE will be considered unexpected if the nature, severity, or frequency of the event is not consistent with the risk information previously described for the study intervention.

8.4.4 Time Period and Frequency for Event Assessment and Follow-Up

The occurrence of an adverse event (AE) or serious adverse event (SAE) may come to the attention of study personnel during study visits and interviews of a study participant presenting for medical care, or upon review by a study monitor. At each study visit, the investigator will inquire about the occurrence of AE/SAEs since the last visit.

Study staff will record all reportable events with start dates occurring any time after informed consent is obtained until 7 (for non-serious AEs) or 30 days (for SAEs) after the last day of study participation. Any significant worsening noted during interim or final physical examinations, electrocardiogram, x-ray filming, any other potential safety assessment required or not required by protocol should also be recorded as a non-serious or serious AE, as appropriate, and reported accordingly.

Abbreviated Title: Effects of leptin in insulin resistance

Version Date: AM N ver. (approved 10/21/20); rev for AM O (5/5/21)

Laboratory Test Result Abnormalities

The following laboratory test result abnormalities will be captured as non-serious AE or SAE as appropriate:

1. Any laboratory test result that is clinically significant or meets the definition of an SAE
2. Any laboratory test result abnormality that required the subject to have study drug discontinued or interrupted
3. Any laboratory test result abnormality that required the subject to receive specific corrective therapy.

It is expected that wherever possible, the clinical rather than laboratory term would be used by the reporting investigator (e.g., anemia versus low hemoglobin value).

Any medical condition that is present at the time that the participant is screened will be considered as baseline and not reported as an AE. However, if the study participant's condition deteriorates at any time during the study, it will be recorded as an AE.

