In a pilot study of two patients with the Rabson-Mendenhall syndromes (caused by biallelic mutations of the insulin receptor), 02-DK-0060, “Efficacy of leptin therapy in severe insulin resistance: a pilot study,” we followed two children with Rabson-Mendenhall on 10 months of recombinant leptin therapy. During the 10 months of leptin therapy, the patients had dramatic improvements (40%) in their fasting hyperinsulinemia and (50%) hyperglycemia, and overall improvements in their %HgbA1c and glucose and insulin tolerance. Three months after the medication was withdrawn, the improvements observed had deteriorated to their pre-trial baseline [1]. A follow up report published in 2013 in 5 patients who participated in the current study demonstrated that A1c decreased from $11.4 \pm 1.1\%$ at baseline to $9.3 \pm 1.9\%$ after 6 months and

9.7±1.6% after 12 months of metreleptin (P=0.007) [2]. In patients treated for 10 years, A1c declined with each cycle of metreleptin and rose with each withdrawal.

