4 STUDY DESIGN

4.1 OVERALL DESIGN

This study is designed to investigate the effect of recombinant leptin on various metabolic and hormonal abnormalities in patients with known or suspected mutations of the insulin receptor gene. These patients have low leptin levels in addition to other metabolic abnormalities. This study utilizes an open-label design, and the accrual ceiling is set at 20 patients. Cumulative changes in each patient will be compared to his/her baseline state after 6 and 12 months. The primary outcome will be assessed after 12 months of study drug. After the patient has completed one year of therapy and has shown metabolic improvement on the medication and the patient desires to continue therapy, the PI at NIH will consider extending therapy on an annual basis. The study medication is supplied through Amryt Pharma, and neither NIH nor Amryt Pharma can guarantee its availability after the study ends.

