6.5 CONCOMITANT THERAPY

If patients are on glucose lowering therapy at the beginning of the study, metreleptin will be added to the existing therapy. Patients' previous therapy will be tapered to prevent hypoglycemia if necessary but doses of glucose lowering medications will not be increased during the first year of the study (at the time the primary outcome is assessed.) Glucose lowering therapies may be adjusted as clinically indicated after the first year of treatment. Patients will be standard clinical instruction about signs and symptoms of and instructions to relieve hypoglycemia.

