8.4.6 Serious Adverse Event Reporting

Following the subject's written consent to participate in the study, all SAEs, whether related or not related to study drug, must be collected, including those thought to be associated with protocol-specified procedures. All SAEs must be collected that occur within 30 days of discontinuation of dosing. The investigator should report any SAE that occurs after these time periods and that is believed to be related to study drug or protocol-specified procedure.

An SAE report should be completed for any event where doubt exists regarding its seriousness. If the investigator believes that an SAE is not related to study drug, but is potentially related to the conditions of the study (such as withdrawal of previous therapy or a complication of a study procedure), the relationship should be specified in the narrative section of the SAE Report Form.

SAEs, whether related or not related to study drug, (including pregnancies) must be reported to United BioSource Corporation (UBC) (a contract research organization contracted by Amryt Pharma) on an SAE Report Form or similar form (e.g. CIOMS, MedWatch) and submitted as soon as possible but not more than 7 calendar days in the event of a death or a life-threatening event or in 15 calendar days for all other SAEs. The SAE report(s) and are to be transmitted via email or confirmed facsimile (fax) transmission to:

SAE Email Address: [contact]

Abbreviated Title: Effects of leptin in insulin resistance

Version Date: AM N ver. (approved 10/21/20); rev for AM O (5/5/21)

If only limited information is initially available, follow-up reports are required. (Note: Follow-up SAE reports should include the same investigator term(s) initially reported). If an ongoing SAE changes in its intensity or relationship to study drug or if new information becomes available, a follow-up SAE report should be sent to the United BioSource Corporation (or designee) using the same procedure used for transmitting the initial SAE report. All SAEs should be followed to resolution or stabilization.

Per NIH HRPP SOP 801, all serious adverse events will be reported to the IRB at the time of annual review if they do not meet the expedited reporting criteria. The PI will report all deaths per the NIH HRPP SOP #801.

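### After treatment ends, non-serious AEs are recorded for 7 days and SAEs not judged related for 30, against a three-month loss of benefit in the pilot, and sections 8.4.4 and 8.4.6 count from different dates

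*Combined protocol and SAP*

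**What the plan says.** - **Collection windows.** Section 8.4.4 records events from consent "until 7 (for non-serious AEs) or 30 days (for SAEs) after the last day of study participation". Section 8.4.6 has its own rule: "All SAEs must be collected that occur within 30 days of discontinuation of dosing".
- **Later SAEs.** Section 8.4.6 continues: "The investigator should report any SAE that occurs after these time periods and that is believed to be related to study drug", or to a protocol procedure. It sets no end date for this.
- **How events are found.** Section 8.4.4 relies on study visits, presentation for medical care and monitor review. The schedule in 1.3 has no post-treatment column. Section 7.1, on stopping the drug, only points to 7.2, on leaving the study.
- **Baseline rule.** Under 8.4.4 a condition already present at screening is not an AE unless it gets worse during the study.
- **What happens on stopping.** Section 2.2 says of the pilot that "we followed two children with Rabson-Mendenhall on 10 months of recombinant leptin therapy", and then: "Three months after the medication was withdrawn, the improvements observed had deteriorated to their pre-trial baseline". Of patients treated for 10 years it says "A1c declined with each cycle of metreleptin and rose with each withdrawal".
- **Why stopping is foreseeable.** Section 4.1 says that "neither NIH nor Amryt Pharma can guarantee its availability after the study ends". Section 10.2 names the supplier's unwillingness to continue as a ground for closing the study.
- **Background treatment.** Section 6.5 says that patients' "previous therapy will be tapered to prevent hypoglycemia if necessary".

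**The concern.** The only interval the protocol gives for loss of benefit is three months, and both windows are shorter. Nothing prompts anyone to ask about events after the last visit. A patient whose background treatment was tapered under 6.5 may also stop metreleptin on less glucose-lowering treatment than at entry.

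At stake is what the safety summary can say about stopping. Loss of glycemic control is a foreseeable consequence, yet it is not among the risks listed in 2.3.1, and 9.4.4 does not separate events after the last dose from those on treatment. A reader of the results could take few recorded events after stopping as reassurance, when little was done to look for them.

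**Working it through.** **Inputs.** Windows of 7 and 30 days (8.4.4; 30 days also in 8.4.6). Interval to observed loss of benefit: three months (2.2), taken as 91 days. The plan gives no coverage figure or reason for the windows, so there is nothing of its own to reproduce.

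**1. Calendar coverage**, if the last dose is also the last day on study. Coverage = window / interval.
- Non-serious AEs: 7/91 = 7.7%, leaving 92.3% uncovered.
- SAEs not judged related: 30/91 = 33.0%, leaving 67.0% uncovered.
- With three months taken as 84 to 92 days: 7.6% to 8.3%, and 32.6% to 35.7%.

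**2. Share of events captured.** This needs an onset pattern, and the documents give none. The patterns below are assumptions, each confined to the 91 days. With w the window and h the half-life of onset in days:
- even onset: w/91
- linearly rising risk: (w/91)²
- front-loaded onset: (1 − 2^(−w/h)) / (1 − 2^(−91/h))

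| Assumed onset | Within 7 days | Within 30 days |
|---|---|---|
| Rising risk | 0.6% | 11% |
| Even | 7.7% | 33% |
| Front-loaded, h = 45 | 14% | 49% |
| Front-loaded, h = 30 | 17% | 57% |
| Front-loaded, h = 14 | 30% | 78% |
| Front-loaded, h = 7 | 50% | 95% |

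Under front-loading, most non-serious events fall outside the window once h exceeds about 7 days, and most SAEs only once h exceeds about 43 days. The SAE column ignores the open-ended reporting of related SAEs, which would raise it.

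**3. The two start dates.** Suppose participation ends k days after the last dose.
- Under 8.4.4, SAE collection ends k + 30 days after the last dose, and non-serious collection ends at k + 7.
- Under 8.4.6, SAE collection ends at day 30 whatever k is.
- The sections agree only when k = 0. For 8.4.4 to reach day 91, k must be at least 91 − 30 = 61 days for SAEs and 91 − 7 = 84 days for non-serious AEs. No off-drug follow-up is described that would produce such a k.

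**4. The baseline rule.** The pilot describes a return to the pre-trial level. Measured against screening, that is no deterioration, and after participation ends it is no longer during the study. A longer window alone could therefore still leave this change unrecorded.

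**The case against.** The strongest reply is that SAE collection does not simply end at 30 days. Section 8.4.6 keeps later related SAEs reportable indefinitely, and 8.4.3.2 counts a temporal relationship as related and tells assessors always to suspect the product. This stands, and it limits the SAE gap to events judged unrelated. The backstop is still passive and depends on the assessor. Section 8.4.3.2 also allows an unrelated call where giving the drug did not cause the event or another cause is established. Section 8.4.6 itself offers withdrawal of earlier treatment as an example of something other than the study drug behind an SAE. Nothing shows which way investigators would decide.

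A reader might infer that most harm from stopping goes unrecorded, and read 92% and 67% as shares of events lost. The documents do not support that. Section 2.2 reports loss of metabolic benefit at one time point in two children, with no adverse events from stopping and no course within the three months. Benefit could have gone within weeks.

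Three further points carry weight:
- Patients who stop for non-response or lost efficacy have little benefit left to lose. The issue lies mainly with stopping for supply, adverse events or patient choice.
- No passage says that the last dose ends participation. For anyone kept on study off drug, the gap under 8.4.4 shrinks.
- Withdrawal safety is not an objective, and the 12-month HbA1c result is unaffected.

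**Conclusion.** The point holds as a modest, inexpensive improvement to safety collection. If dosing and participation end together, the plan as written actively covers about 8% of the three-month interval for non-serious AEs and about 33% for SAEs not judged related, with no scheduled contact in the remainder. For non-serious AEs, at most about half are captured under any pattern tabulated. For SAEs the captured share runs from about 11% to 95% before late related reports are added, so no claim about most SAEs can be made. The three-month figure rests on two children, supported in direction but not in timing by the A1c rise on each later withdrawal. Separately, and whatever view is taken of the windows, 8.4.4 and 8.4.6 start from different events and must be reconciled.

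**What to change.** - **8.4.4 and 8.4.6:** state one common rule. Collect AEs and SAEs regardless of relatedness until the later of about three months after the last dose, or the present 7 days (non-serious) or 30 days (serious) after participation ends. Counting from the last dose alone could shorten collection for anyone who stays on study off drug. Keep the open-ended reporting of related SAEs.
- **Contact:** plan one telephone or telehealth contact at about three months after the last dose, with a local HbA1c where available, for participants who can be reached. The remote provisions in 1.3 can be extended to cover it.
- **Baseline rule in 8.4.4:** say that worsening of glycemic control from the last on-treatment value is recorded despite the screening-baseline rule.
- **9.4.4:** report events after the last dose as a separate line.
- **2.3.1:** list loss of glycemic control after stopping.

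The cost is a few sentences and one contact per patient who stops, at most 20 under the accrual ceiling. Follow-up becomes slightly longer, reach will be incomplete among those who withdraw or are lost, and a few more disease-related events will need reporting. No dose or treatment rule changes.
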